8.10 Product Accountability

In accordance with federal and local regulatory requirements, the Investigator and designated site personnel must document the amount of investigational product dispensed to study participants, the amount returned by study participants, and amount received and returned to the sponsor, when applicable. Product accountability records must be maintained throughout the course of the trial. Any quality issue noticed with the receipt or use of an IP (deficient IP in condition, appearance, pertaining documentation, labeling, expiry date, etc.) should be promptly reported to the Sponsor, who will initiate a complaint procedure. All investigational product must be stored in a secure locked room with access limited to the Investigator and designated site personnel. Study product is to be stored in a refrigerator between 2-8°C. Maintenance of a temperature log is required. Under no circumstances will the Investigator allow IP to be used other than as directed by this Clinical Trial Protocol, or dispose of IP in any other manner.

8.11 Unblinding Procedures

The Investigator may unblind a participant's treatment assignment only in the case of emergency or in the event of a serious medical condition when knowledge of the study treatment is essential for the appropriate clinical management or welfare of the participant, as determined by the Investigator. It is preferred (but not required) that the Investigator first contacts the Medical Monitor to discuss options before unblinding the participant's treatment assignment. The Investigator must notify the Sponsor as soon as possible when a participant's treatment assignment is unblinded without revealing the treatment assignment of the unblinded participant unless that information is deemed important for the safety of participants currently in the study. The date and reason for the unblinding must be documented in the participant's study record. The Medical Monitor may unblind the treatment assignment for any participant with an SAE. If the SAE requires that an expedited regulatory report be sent to one or more regulatory agencies, a copy of the report, identifying the participant's treatment assignment, may be sent to clinical Investigators in accordance with local regulations and/or sponsor policy.

8.12 Retrieval and Destruction of Investigational Product

All partially used or unused treatments will be returned to the site as brought by study participants. A detailed IP log of the returned IP shall be established.

The site will not destroy unused IP unless the Sponsor provides written authorization to the contrary. All used and unused bottles will be shipped to the authorized drug depot at the end of the study.

8.13 Concomitant and Excluded Therapies

Any medication or vaccine (including over-the-counter or prescription medicines, vitamins, and/or herbal supplements) that the subject is receiving within 30 days prior to screening and through the final study visit will be recorded on the appropriate CRF) along with:

- Reason for use.
- Dates of administration including start and end dates.
- Dosage information including dose and frequency.

Any medications started during the study (including "as needed" medications) will be recorded in the concomitant medication list as soon as the Investigational Site will become aware of the medication being added.

Details of any medication taken by the subject outside of the study center will be reviewed by the Investigator or designee on each study center visit. The Medical Monitor should be contacted if there are any questions regarding concomitant or prior therapy.

A list of excluded medications/therapy is provided in Appendix B.

Previous treatment of atopic dermatitis must be recorded irrespective of the term it was given. Acetaminophen is permitted for use any time during the study. Other concomitant medication may be considered on a case-by-case basis by the Investigator in consultation with the Medical Monitor.

Concomitant therapies include any therapies (including over-the-counter medications) used by a subject from initiation of study drug treatment through the follow-up period. A record of all medications used will be maintained for each subject throughout the study. Reported information will include a description of the type of drug, treatment period, dosing regimen, the route of administration, and drug indication.

8.13.1 Permitted Medications

Subjects using oral contraceptives, hormone-replacement therapy, or other maintenance therapies that are not Excluded Therapies (Appendix B) may continue their use during the study.

Stable doses of the following therapies for pruritus and/or atopic dermatitis will be allowed as adjunctive therapies during the study:

- Oral H1 antihistamines
- Bland emollients

A detailed guideline will be shared with the sites and subjects to ensure consistency in study medication treatment application and relation to body washing, emollient use, and other chemical exposure to skin.

Low- or mid-potency topical corticosteroids will be allowed per subjects' usual medication, frequency, and dose throughout the study from screening to washout, treatment, and follow-up periods as rescue medication up to 7 days per month.

Subjects using any of these adjunctive therapies should maintain their regimen without clinically significant changes in type, dose or frequency throughout the screening, treatment, and follow-up periods.

All participants will be screened for concomitant medications prior to inclusion into the study. Any concomitant medication to treat adverse events will be recorded in the Concomitant Medication section of the eCRF.

8.13.2 Excluded Therapies

Therapies and medications that are excluded from the initial Screening visit through the follow-up period are listed in Appendix B.

8.14 Rescue Medications

8.14.1 Rescue Medication Permitted During the Study

Over the course of the study, the Investigator will monitor and evaluate subject's condition and determine whether rescue therapy may be necessary. The use of medications to treat a subject's atopic dermatitis during the study will be permitted if a medical professional determines that it becomes medically necessary. Such rescue treatment should not exceed 7 days per month for the duration of the trial (screening, washout, treatment, and follow-up), e.g., no more than 3 days total during the 2 week washout period, no more than 7 days total during the 4 week follow-up period. If a subject requires treatment for more than 7 days per month or requires systemic therapy, they may be discontinued from the study. Medications permitted are listed in Table 8.1.

In the event of an atopic dermatitis or pruritus exacerbation in between visits, subjects should contact study staff as soon as they are able. Subjects should seek approval on the use of rescue medications. In the event that the subject did not notify the study staff, every effort should be made by the subject to contact the PI or study staff as soon as feasible. The details of the medication should be recorded in the eDiary and transferred to the CRF. Details recorded should include medication name, date of administration, dosage, and number of applications.

Table 8.1 Permitted Rescue Medication

Class 4 – Mid-strength			
Clocortolone pivalate (0.1%)	Cloderm® Cream		
Mometasone furoate (0.1%)	Elocon® Cream		
Triamcinolone acetonide (0.1%)	Aristocort® A Cream, Kenalog® Ointment		
Betamethasone valerate (0.1%)	Valisone Ointment		
Fluocinolone acetonide (0.025%)	Synalar® Ointment		
Class 5 – Lower Mid-strength			
Fluticasone propionate (0.05%)	Cutivate® Cream/Cutivate Lotion		
Prednicarbate (0.1%)	Dermatop® Cream		
Hydrocortisone probutate (0.1%)	Pandel® Cream		
Triamcinolone acetonide (0.1%)	Aristocort A Cream, Kenalog Lotion		
Fluocinolone acetonide (0.025%)	Synalar Cream		
Class 6 – Mild			
Alclometasone dipropionate (0.05%)	Aclovate® Cream/Ointment		
Desonide (0.05%)	Verdeso™ Foam, Desonate Gel™		
Triamcinolone acetonide (0.025%)	Aristocort A Cream, Kenalog Lotion		
Hydrocortisone butyrate (0.1%)	Locoid Cream/Ointment		
Fluocinolone acetonide (0.01%)	Derma-Smoothe/FS® Scalp Oil, Synalar Topical Solution		
Class 7 – Least potent			
Hydrocortisone (2%/2.5%)	Nutracort® Lotion, Synacort Cream		
Hydrocortisone (0.5 to 0.1%)	Cortaid® Cream/Spray/Ointment and many other over-the-counter products		

8.14.2 Use of Excluded Therapies During the Treatment Period

Subjects who use an excluded therapy during the treatment period for treatment of atopic dermatitis or pruritus outside of the rescue medication allowance will be discontinued from study drug treatment, with the following exception:

• Subjects who require short treatment for indications other than atopic dermatitis or pruritus (up to a total of 3 days over the treatment period) with sedatives, tranquilizers, opioids, and/or topical therapies will not be required to discontinue from study drug treatment.

Use of any excluded therapies will be recorded for subjects who receive them.

8.15 Handling of Investigational Product

Subjects will receive study IP in 30 ml white bottles. Each bottle will be anticipated for use over 10 days and brought to all study appointments. The IP bottle can be kept at room temperature while in use by the subject.

Subjects will be asked not to subject the treatment kit to conditions which are unnatural or harmful to the product, such as excessive heat (temperatures over 77°F (25°C)) and freezing temperatures (below 32°F (0°C)). Subjects may travel with their study medication but should not leave it in a hot car, outside in the cold temperatures, etc. Subjects will also be asked not to tamper or cause damage to IP.

9 CONTRACEPTION REQUIREMENTS

Effective contraception is required for all women physiologically capable of becoming pregnant during study participation. Women of child-bearing potential must agree to use an acceptable form of contraception for up to 2 weeks after the study completion as detailed. Women of childbearing potential are defined as any female who has experienced menarche and who is NOT permanently sterile (e.g., by tubal ligation) or postmenopausal. Postmenopausal is defined as 12 consecutive months with no menses without an alternative medical cause.

Effective contraception methods include:

- Use of oral, injected or implanted hormonal methods of contraception or placement of an IUD or IUS or other forms of hormonal contraception that have comparable efficacy, for example hormone vaginal ring or transdermal hormone contraception
- Use of barrier methods (i.e., condom, diaphragm) used with a spermicide (i.e., foam, cream, or gel that kills sperm)
- Total abstinence (when this is in line with the preferred and usual lifestyle of the study participant).

Periodic abstinence (i.e., calendar, ovulation, symptothermal, postovulation methods) and withdrawal are not acceptable methods of contraception.

Male participants of the study who are having sexual intercourse with a woman who can become pregnant must use an acceptable form of birth control while participating in the study. Additionally, male participants are expected to inform their female partners of their participation in a research study of an investigational drug, the effects of which on a fetus and on a pregnant woman are unknown. Male participants will also be expected to provide their female partners with the contraception requirements information previously described and the study doctor's contact information for questions.

Payment for all aspects of obstetrical care, child-or related care will be the study participant's responsibility.

In case of pregnancy, Investigational Product should be discontinued and the Sponsor should be informed immediately. Follow-up of the pregnancy will be mandatory until the outcome is available

10 STUDY PROCEDURES

10.1 Pre-screening procedures

Study subjects will be recruited from among participating hospitals, clinics, and diagnostic centers or from general population under the responsibility of a participating Investigator. Prior to initiation of the recruitment phase, participating Investigators will identify a pool of potential study subjects. Each of these centers will identify potentially eligible patients in advance, by either reviewing past medical records and diagnoses, screening in clinics, referral from other physicians, or other sources of recruitment, to identify those aged 18 to 65 with clinical diagnosis of mild or moderate Atopic Dermatitis. Medical records from patient's dermatologist or primary care physician to confirm the diagnosis are optional. Verbal confirmation of the diagnosis present for > 12 months is sufficient to fulfill this criterion.

10.2 Informed Consent Procedures

Eligible participants may only be included in the study after providing a consent using the IRB-approved informed consent form. Informed consent must be obtained before conducting any study-specific procedures (i.e., all of the procedures described in the protocol). The process of obtaining informed consent should be documented in the participant's source documents. The date of signing of informed consent (and withdrawal, if later withdrawn) should be documented in the eCRF

10.3 Study Assessments

Study activities will take place according to the Time and Events table (Appendix A).

Demographics and a complete medical history will be recorded during the Screening period. The medical history will include a complete review of all current diseases and their respective durations and treatments

10.4 Inclusion procedures

Once all inclusion/exclusion criteria are fulfilled, the patient becomes eligible for randomization and inclusion into the treatment period. Treatment allocation will be performed as stated above

in Section 8.5. Study medication will be delivered as stated in Section 8.6. Patients will be counseled on product application and eDiary completion.

10.5 Timing of patient's visits to the clinic

Patients will be asked to report to the clinic for their scheduled appointments. If a subject is unable to schedule an appointment within the required time frame, study staff will be asked to reschedule the patient to a day when they are able to come in within predetermined time frame.

10.6 Description by type of visit

10.6.1 Screening Visit (-21 to -14) – Visit 1

- informed consent completed and signed
- inclusion and exclusion criteria
- demographic data
- medical/surgical history
- concomitant medications
- physical exam
- vital signs
- blood for clinical chemistry, serology and hematology
- urine pregnancy test (for women of childbearing potential)
- NRS assessment
- POEM questionnaire
- Pruritus 5-D questionnaire
- IGA scoring assessment
- EASI scoring assessment
- study counseling
- start eDiary
- start AE monitoring

10.6.2 Washout Phase (-14 to -1)

For those subjects who meet the eligibility criteria at the Screening visit and is determined by the Principal Investigator to be eligible for the study after the safety labs testing results are available, subjects will be notified by telephone to start the Washout period phase. Subjects will be allowed to use their regular emollients if needed but will be asked to stop using bleach or vinegar baths.

Stable doses of the following therapies for pruritus and/or atopic dermatitis will be allowed as adjunctive therapies during the study:

- Oral H1 antihistamines
- Bland emollients

A detailed guideline will be shared with the sites and subjects to ensure consistency in study medication treatment application and relation to body washing, emollient use, and other chemical exposure to skin.

Low- or mid-potency topical corticosteroids will be allowed per subjects' usual medication, frequency, and dose during the washout period but no more than 7 days per month as rescue medication.

Subjects using any of these adjunctive therapies should maintain their regimen without clinically significant changes in type, dose or frequency throughout the screening, treatment, and follow-up periods.

Subjects will be prohibited from using Excluded Medications/Therapy listed in Appendix B.

- phone call to subjects
- study counseling

10.6.3 Study Day 0-Baseline visit (0) – Visit 2

- inclusion and exclusion criteria
- concomitant medications
- medical history
- vital signs
- urine pregnancy test (for women of childbearing potential)
- NRS assessment
- POEM questionnaire
- Pruritus 5-D questionnaire
- IGA scoring assessment
- EASI scoring assessment
- allocation of a randomized treatment kit number via IWRS
- delivery of the corresponding Investigational Product
- obtain study medication weight for Investigational Product compliance
- first application of Investigational Product (under medical supervision)
- study counseling
- eDiary review
- recording of AEs if any

10.6.4 Day 5- Phone call to patient

The Day 5 visit is a telephone visit that occurs 5 days (±2 days) after the Baseline visit. Study staff will discuss IP application with the subject, answer any questions and counsel the subject on any other matters related to the study.

- phone call to subjects
- application of study drug
- study counseling

10.6.5 Day 14 and Day 28 study visits – Visit 3 and Visit 4

- concomitant medications
- vital signs
- blood for clinical chemistry and hematology (Day 28)
- urine pregnancy test (for women of childbearing potential) (Day 28)
- NRS assessment
- POEM questionnaire
- Pruritus 5-D questionnaire
- IGA scoring assessment
- EASI scoring assessment
- obtain study medication weight for Investigational Product compliance
- dispense investigational product to patient (Day 14)
- collect study medication
- application of study drug
- eDiary
- study counseling
- recording of AEs if any

10.6.6 Day 56-End of Study Visit – Visit 5

- concomitant medications
- vital signs
- physical exam
- urine pregnancy test (for women of childbearing potential)
- NRS assessment
- POEM questionnaire
- Pruritus 5-D questionnaire
- IGA scoring assessment
- EASI scoring assessment
- eDiary
- recording of AEs if any

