8.9 Study Drug Discontinuation

Subjects will be discontinued from study drug treatment in the following events:

- The subject experiences a Grade 2 or higher treatment emergent AE that is assessed as likely related to study drug
- The subject receives treatment with an excluded therapy or has a clinically significant change in dose or frequency of allowed adjunctive therapies during the treatment period
- The female subject becomes pregnant or female partner of a male subject becomes pregnant or is breastfeeding

Discontinuation from study drug treatment may also occur for any of the following reasons:

- Subject decision to discontinue study drug treatment, or subject decision to withdraw consent from the study
- Any medical condition that may jeopardize the subject's safety if study drug is continued, in the investigator's and/or Sponsor's opinion
- Discontinuation is deemed to be in the best interest of the subject, in the investigator's and/or Sponsor's opinion

Subjects who discontinue treatment with study drug prior to completing the treatment period will have an ETD visit within 7 days after their last dose of study drug in addition to a follow-up visit

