12.4.2 Adverse Events

All adverse events (AEs) recorded during the study through the date of randomization through 28 days after the last dose of study drug will be analyzed.

Adverse events will be summarized by treatment group using the Medical Dictionary for Regulatory Activities (MedDRA) system organ class and preferred term. Separate tabulations will be produced for all treatment-emergent AEs (TEAEs), treatment-related AEs (those considered by the Investigator as at least possibly drug related), SAEs, discontinuations due to AEs, and AEs \geq Grade 3 severity. By-subject listings will be provided for any deaths, SAEs, and AEs leading to discontinuation.

AE's will be summarized using incidence rates. Therefore, each subject will only contribute once for a given adverse event SOC or PT.

Any treatment emergent AEs related to local safety (e.g., erythema, edema, induration, vesiculation, etc.) will be collected by the investigator during scheduled clinic visits. In addition, solicited local adverse reactions (e.g., itching, new rash, pain, tenderness, stinging, skin color change, etc.) and severity from subjects will be collected during the first week of treatment using eDiary to inform local skin tolerability.

A summary of the incidence of any adverse event, SAE, and adverse events leading to discontinuation will be presented. Summaries will display, by treatment group, the incidence of patients with events, the frequency of patients with events within each primary system organ class and by preferred terms. For each preferred term and each system organ class a patient will

be counted only once. For summaries on severe or drug-related AE, for a given patient, the highest severity or relationship for a specific preferred term will be considered.

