13.3 Time-period, Frequency, and Method of Detecting AEs and SAEs

All AEs occurring after administration of the first dose of study medication and on or before the final assessment must be reported as AEs. All AEs must be recorded irrespective of whether they are considered drug-related.

At each assessment in the period defined above, AEs will be evaluated by the Investigator and recorded.

Any AEs already documented at a previous assessment and designated as ongoing, should be reviewed at subsequent assessments as necessary. If these have resolved, this should be documented. Changes in intensity or frequency of AEs should be recorded as separate events (i.e., a new record started).

The recording of AEs and SAEs are described in Section 13.4 ("Recording of AEs and SAEs").

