									labs are finalized. Call on Day 5 will be made to counsel subjects on the use of IP and eDiary recordings, as well as answer any questions.
Collect study drug					X	X		X	
Study counseling	X	X	X	X	X	X			Subjects will be counseled at each visit on the appropriate use of IP, eDiary entries and use.
AE monitoring	X		X		X	X	X	X	AE will be monitored from screening to follow-up. After informed consent, but prior to study drug administration, only SAEs caused by a protocolmandated intervention will be collected

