2.2 Schedule of Activities

| Visit Name# | Screening | Washout | Baseline | Day 5 | Day 14 | Day 28 | Day 56 | Early |
|------------------------------------|------------|-----------|----------|-------|----------|---------------------------------------|----------|------------|
| | L C | phase | Day 0 | 2 | (Week 2) | (Week 4) | (Week 8) | Terminatio |
| | | 1 | 2 | | , , | , , , , , , , , , , , , , , , , , , , | × , | n Visit |
| Visit Number | V1 | | V2 | | V3 | V4 | V5 | |
| Visit Window in days | -21 to -14 | -14 to -1 | 0 | +/-2 | +/-2 | +/-2 | +/-3 | |
| Informed Consent | Х | | | | | | | |
| Inclusion / Exclusion Criteria | X | | Х | | | | | |
| Demographics | Х | | | | | | | |
| Medical History | Х | | Х | | | | | |
| Concomitant Medications | Х | | Х | | X | Х | Х | X |
| Physical Exam | X | | | | | | X | X |
| Vital Signs | X | | Х | | X | Х | Х | X |
| eDiary | X | Х | Х | Х | X | Х | Х | X |
| POEM | X | | Х | | X | Х | Х | X |
| 5-D Pruritus Scale | X | | Х | | X | Х | Х | X |
| IGA | Х | | Х | | X | Х | Х | X |
| EASI | Х | | Х | | X | Х | Х | X |
| Itch Numeric Rating Scale (NRS) | X | Х | Х | Х | X | Х | Х | X |
| Clinical Labs | X | | | | | Х | | X* |
| Urine pregnancy test for WOCBP | X | | Х | | | Х | X | Х |
| IWRS | | | Х | | | | | |
| Investigational Product compliance | | | Х | | X | Х | | X |
| Dispense study drug | | | Х | | X | | | |
| Application of study drug | | | Х | Х | X | Х | | |
| Phone call to subjects | | Х | | Х | | | | |
| Collect study drug | | | | | X | Х | | X |
| Study counseling | Х | Х | Х | Х | Х | Х | | |

CLINICAL RESEARCH OPTIMIZED™

Protocol: PRB244-01 Confidential STATISTICAL ANALYSIS PLAN

Version 3.0 12-Jan-22

| Visit Name# | Screening | Washout | Baseline | Day 5 | Day 14 | Day 28 | Day 56 | Early |
|----------------------|------------|-----------|----------|-------|----------|----------|----------|------------|
| | | phase | Day 0 | | (Week 2) | (Week 4) | (Week 8) | Terminatio |
| | | | | | | | | n Visit |
| Visit Number | V1 | | V2 | | V3 | V4 | V5 | |
| Visit Window in days | -21 to -14 | -14 to -1 | 0 | +/-2 | +/-2 | +/-2 | +/-3 | |
| AE monitoring | X | | X | | X | X | X | X |

#: Comments/clarification to visits in table below.

*: if visit occurs before Day 28

.....

| Protocol: PRB244-01 | STATISTICAL ANALYSIS PLAN |
|---------------------|---------------------------|
| Confidential | |

Version 3.0 12-Jan-22

| Visit Name | Comments/Clarification |
|---------------------------------|--|

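### The Day 5 call has no adverse-event item: non-local events get no scheduled staff inquiry until Week 2, and tolerability diary scores have no timed review

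*Protocol*

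**What the plan says.** Protocol 10.6.4 calls the Day 5 contact a visit: "The Day 5 visit is a telephone visit that occurs 5 days (±2 days) after the Baseline visit". It describes the content as follows: "Study staff will discuss IP application with the subject, answer any questions and counsel the subject on any other matters related to the study". The item list beneath has no AE entry. The Appendix A comment gives the same purpose: "Call on Day 5 will be made to counsel subjects on the use of IP and eDiary recordings, as well as answer any questions".

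The AE row in SAP 2.2 reads "AE monitoring | X | | X | | X | X | X | X". The second and fourth cells, Washout and Day 5, are empty; the Appendix A row shows the same marks. The visit lists for Baseline, Day 14, Day 28, Day 56 and Early Termination (Protocol 10.6.3, 10.6.5, 10.6.6, 10.6.8) all include recording of AEs.

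Protocol 13.3, for the period that starts with the first dose, says: "At each assessment in the period defined above, AEs will be evaluated by the Investigator and recorded".

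For local reactions there are two routes. Under Protocol 12.4.2, local treatment-emergent AEs "will be collected by the investigator during scheduled clinic visits", and solicited local reactions are also collected by eDiary in the first week. Appendix G defines five items, each graded 0 to 3: redness or color change, itching, burning or stinging, pain or tenderness, and rash. SAP 7.5.2 leaves it to the investigator to decide whether such a symptom is recorded as an AE, and gives no time for that decision.

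**The concern.** Two safety rules work on AEs that the investigator has assessed. Protocol 8.9 lists among the events that end study drug in a subject: "The subject experiences a Grade 2 or higher treatment emergent AE that is assessed as likely related to study drug". Protocol 7.3 pauses the study for safety review on counts of deaths, SAEs and AEs considered related. Neither rule acts on a diary score that nobody has read, or on an event nobody has asked about.

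Staff already speak to every subject in the first week of treatment, but the call has no AE question and no look at diary content. Events outside the five diary items therefore rely on the subject raising them. Protocol 7.3 itself notes that localized infection and cellulitis can occur in this disease; infection is not an Appendix G item. Non-local events from the first week may also be recalled and dated less well at Week 2. That is an inference, since the documents give no data on it.

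**Working it through.** **Schedule.** Scheduled contacts from first dosing onward, and whether an AE item is listed:

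- Baseline: yes
- Day 5 call: no
- Day 14: yes
- Day 28: yes
- Day 56: yes
- Early Termination: yes

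Day 5 is the only gap. The one diary review whose purpose is spelled out is at Baseline, to determine eligibility (Appendix A comment). The Day 5 list in 10.6.4 has no diary item.

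**Inputs.**

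- Applications: 2 per day (Protocol 8.7).
- Day 5 call: Day 5 ± 2, so Day 3, 5 or 7 (Protocol 10.6.4).
- Week 2 visit: Day 14 ± 2, so Day 12, 14 or 16 (Appendix A; SAP 2.2).
- End of tolerability diary: SAP study Day 7, which is protocol Day 6 (SAP 6.4).

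**The plan's own figure.** 2 per day × 28 days = 56, the number of dosing entries in SAP 7.5.1. It reproduces.

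**Call to Week 2 visit.** Applications = 2 × (visit day − call day):

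| Call day | Visit Day 12 | Visit Day 14 | Visit Day 16 |
|---|---|---|---|
| 3 | 18 | 22 | 26 |
| 5 | 14 | 18 | 22 |
| 7 | 10 | 14 | 18 |

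Nominal 2 × (14 − 5) = 18; minimum 2 × (12 − 7) = 10; maximum 2 × (16 − 3) = 26. Counting both doses on both end days adds 2, so the maximum becomes 28.

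**Cross-check from an event on Day 1.** To the Week 2 visit: 2 × (12 − 1) = 22, 2 × (14 − 1) = 26, 2 × (16 − 1) = 30. To the call: 2 × (3 − 1) = 4, 2 × (5 − 1) = 8, 2 × (7 − 1) = 12. The nominal difference, 26 − 8 = 18, agrees with the table.

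**After the diary ends.** Applications to the Week 2 visit: 2 × (12 − 6) = 12, 2 × (14 − 6) = 16, 2 × (16 − 6) = 20. In this stretch not even the five local items are solicited.

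**The case against.** The strongest reply is that subjects are asked early. Five local symptoms are solicited and graded every day of the first week, and the Protocol synopsis treats local reactions as a solicited AE of special interest. Local tolerability is its own endpoint, built on dated entries, so it does not rest on two-week recall. This stands. A reader might infer that early reactions go unasked until Week 2, or that 12.4.2 confines local AEs to clinic visits. Neither is right: the sentence in 12.4.2 that follows the one on clinic visits adds the eDiary.

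Second, 13.3 speaks of assessments, and nothing defines a counseling call as one. The Day 5 contact has no visit number. Against that, 10.6.4 calls it a visit, and Appendix A marks eDiary and itch NRS in its column, although those marks may reflect only daily home entry. A reader might infer a plain breach of 13.3. The text supports only an ambiguity that needs reconciling.

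Third, Section 13 requires AEs to be recorded whenever staff learn of them, Appendix A describes monitoring as running through to follow-up, 8.14.1 tells subjects to contact staff about an exacerbation between visits, and unscheduled visits are available. All true, but each of these routes waits for the subject to speak up.

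Fourth, a reader might quote 30 further applications. That needs an event on Day 1 and a visit at the far edge of its window, and it is not the interval that asking at the call would change.

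**Conclusion.** The point holds in a limited form, as a cheap improvement. Day 5 is the only scheduled contact from first dosing onward without an AE item. Two gaps follow: non-local AEs have no scheduled staff inquiry between Baseline and Day 12 to 16, and the first-week tolerability scores have no stated review time. In that interval the rules in 7.3 and 8.9 depend on volunteered events or an unscheduled diary review. Asking at the call would bring the inquiry forward by a nominal 18 applications, range 10 to 26.

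These figures assume twice-daily use as planned and contacts inside their windows. The call is planned for all of the approximately 576 randomized subjects, but that is the reach of the schedule, not a count of subjects harmed. The gap matters only where an early event is neither volunteered nor picked up from the diary, and the documents give no rate for that.

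**What to change.** In Protocol 10.6.4, add to the Day 5 call the AE-recording item already used in the other visit lists, together with a review of the tolerability diary entries to date. Mark AE monitoring in the Day 5 column of Appendix A and SAP 2.2. Management of any event found stays with the existing rules.

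Declaring that the call is not an assessment under 13.3, and separately setting a diary review time, would also make the text consistent. It would still leave non-local AEs without a staff inquiry before Week 2.

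The cost is a few minutes in a call that is already made, plus one mark in each schedule. Reported AE rates may rise slightly; because the call is the same in every arm, the rise would be expected in all three.
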